6.3 MEASURES TO MINIMIZE BIAS: RANDOMIZATION AND BLINDING

The randomization scheme will be generated by the study statistician and stored within the study database. The database will be configured so that blinded study personnel (e.g., those conducting follow-up assessments) will not have access to randomization information. The participants will not be notified of randomization assignment until all baseline assessments are complete. In addition an individual participant's randomization assignment will not be known to any study personnel until baseline assessments are complete. Randomization will be stratified according to gender and presence of self-reported pain (≥3 on a 10 point scale) in any lower extremity joint (hip, knee or ankle) in addition to the surgical knee, to ensure that the groups are balanced in these respects.

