8 STUDY ASSESSMENTS AND PROCEDURES

8.1 ENDPOINT AND OTHER NON-SAFETY ASSESSMENTS

Measures will be collected at baseline, 3 months and 6 months by a trained research assistant blinded to randomization assignment. Participants will be paid \$50 for completing baseline questionnaire and \$15 for wearing and returning an accelerometer. Then, up to \$40 at 3 month and 6 month time point: \$25 for completing questionnaires and functional measures and \$15 for wearing and returning an accelerometer. Due to COVID-19 safety measures, we may conduct a briefer set of measures focused on the primary functional assessments. We will explain to the participant during the consent process that the measures may

be more limited in order to minimize in-person visit time. Also, we may schedule a time to call the participant after the in-person visits (at baseline and 3 month and 6 month follow-up) to complete the questionnaires over the phone.

Efficacy (Aims 1 and 2)

Co-Primary Efficacy Outcome: Objectively Assessed Physical Activity (accelerometer). Our specific primary outcome of interest is MVPA per week, since this corresponds to DHHS recommendations and is a known predictor of outcomes in patients with OA ⁷. We will also examine step counts, minutes of any PA and sedentary minutes as secondary outcomes ^{72,73}. Participants will wear the waist-worn Actigraph GT3X+ (Pensacola, FL) for 7 days ⁷⁴. Following previously established thresholds, outcomes will only be computed for participants who wear the accelerometer for 4+ days with 10+ hours of wear. Accelerometers will be given to participants during in-person visits at each time point and mailed back to the study team, using our procedures from prior studies that have resulted in very high adherence rates (89-93%). If participants are not able to complete follow-up assessments in person but complete questionnaires by telephone, we may mail an accelerometer for wear and return via mail. Accelerometer data will be processed using standard procedures ⁷⁵⁻⁷⁸

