Data capture via video cameras discontinued in December 2021 Three high speed cameras will be used to record participants completing the function tests. All cameras will be placed on tripods held 60 cm off the floor. One camera will be placed facing the participant and 150 cm beyond the line in which they turn during the TUG. The other two cameras will be placed to the left and right of the middle of the TUG path approximately 350 cm away from the path. Participants will be equipped with 6 reflective markers, which will be placed bilaterally over the lateral aspect of the femoral epicondyle, in the middle of the shank in-line with the lateral femoral epicondyle and lateral malleoli, and in the middle of the thigh in-line with the lateral femoral epicondyle and greater trochanter. Each camera will be equipped with an external light source (flash), which will cause the reflective markers to shine very brightly and be easily tracked throughout the video. The cameras will collect

wide view videos at 120 frames per second. The wide view video will result in a 'Fish-Eye' effect in the video data, which will be corrected and converted to a linear image using previously developed methods_{23, 26} and the individual cameras lens coefficients. Each marker will be tracked in both the frontal and sagittal view videos after de-warping the fish-eye effect. The XY position of each marker will be used to create knee angles. Before movement trials, a 1 second static trial will be recorded from both views, and the knee angle during quiet stance will be used to normalize knee angle during the movement trials (i.e. knee flexion and valgus will be considered zero during quiet stance).

Balance. We are conducting a limited set of tests due to COVID precautions. We will administer two tests from the Berg Balance Scale: tandem stance and 10 sec single leg stance ⁸⁷. We will also administer one test from the Brief Balance Evaluation Systems Test: Stance With Eyes Closed, on Foam Surface ⁸⁸.

Knee injury and Osteoarthritis Outcome Score (KOOS). The KOOS is a widely used and validated patient-reported outcome that includes five separately scored subscales (42 items total): pain, symptoms, activities of daily living, sports and recreation, and knee-related quality of life ⁹⁰. The KOOS pain subscale will also be assessed at each intervention visit, so that we can assess potential associations between pain and PA.

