9.4 STATISTICAL ANALYSES PLAN

Preliminary analyses will include generating descriptive statistics for demographic variables, as well as baseline characteristics and follow-up measures. This includes means and standard deviations for continuous variables, and frequencies and percentages for categorical variables. Ranges will also be examined for outliers and to ensure data integrity. Demographics and baseline characteristics will also be described separately by randomized group. Statistical tests will be performed to compare each of these by randomized group to determine the extent of random imbalance by t-test of chi-square testing, as appropriate. However, the p-values generated by these tests are considered as descriptive rather than as inferential. We would

expect some imbalance between the groups by random chance, owing to the limited sample size. Variables exhibiting imbalance may be considered as covariates in the statistical models described below.

The co-primary outcome of MVPA will be analyzed across the follow-up time points through a general linear mixed model (GLMM). Specifically, the MVPA values at 8 weeks and at 6 months for a given patient will form their response vector for this model. Fixed effects for the primary model will include an indicator for PAS group, an indicator for the 6-month follow-up time point, their interaction (group by time), and baseline MVPA value; a supporting model will also include any covariates that exhibit random imbalance between groups at baseline. Random effects for patients will account for the within-patient correlation induced by the repeated measures design. Formal statistical testing of the group by time interaction term will provide assessment for whether efficacy varies by follow-up time point. A term representing the interaction of PAS-by-baseline value will be included and tested to explore whether participants' starting point might impact how much they improve; it will be removed if non-significant attention. Statistical contrasts will be constructed in order to estimate the effect of PAS versus attention control, separately at 8 weeks and at 6 months; these estimates will inform the sample size estimation of the subsequent trial. Estimated correlations among follow-up time points will also be useful in this regard.

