The approach outlined above will be repeated for the co-primary outcome of peak joint loading symmetry during gait, through fitting a separate GLMM. The main difference will be to include walking speed as an additional covariate, as justified in the research strategy. Secondary outcomes will also be analyzed using the same approach, each with its own GLMM.

An exploratory analysis will include KOOS pain scores as a (time-dependent) main effect, as well as their interaction with PAS, to evaluate whether this variable has an impact on intervention effects. This exploratory analysis will be repeated, but using participant-specific changes in KOOS pain scores, to examine how our primary outcomes (MVPA and peak load symmetry during walking) are associated with those changes.

If any of the co-primary or secondary outcomes exhibit distributions that deviate markedly from normality, alternatives will be considered. First, transformations, such as the natural logarithm, will be applied in an attempt to normalize the distribution. If this is not successful in remedying the non-normality, alternatives such as categorizing the variable and applying appropriate categorical data analysis, such as logistic mixed models (with a similar specification as described above for the GLMMs) or logistic models utilizing generalized estimating equations methodology can be fitted.

A two-sided 0.05 significance level will be applied to each co-primary outcome, as well as each secondary outcome; no adjustment for multiple comparisons will be applied. This is consistent with the trial's objective as a pilot study to generate estimates useful for the large-scale trial to follow.

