expect some imbalance between the groups by random chance, owing to the limited sample size. Variables exhibiting imbalance may be considered as covariates in the statistical models described below.

The co-primary outcome of MVPA will be analyzed across the follow-up time points through a general linear mixed model (GLMM). Specifically, the MVPA values at 8 weeks and at 6 months for a given patient will form their response vector for this model. Fixed effects for the primary model will include an indicator for PAS group, an indicator for the 6-month follow-up time point, their interaction (group by time), and baseline MVPA value; a supporting model will also include any covariates that exhibit random imbalance between groups at baseline. Random effects for patients will account for the within-patient correlation induced by the repeated measures design. Formal statistical testing of the group by time interaction term will provide assessment for whether efficacy varies by follow-up time point. A term representing the interaction of PAS-by-baseline value will be included and tested to explore whether participants' starting point might impact how much they improve; it will be removed if non-significant attention. Statistical contrasts will be constructed in order to estimate the effect of PAS versus attention control, separately at 8 weeks and at 6 months; these estimates will inform the sample size estimation of the subsequent trial. Estimated correlations among follow-up time points will also be useful in this regard.

The approach outlined above will be repeated for the co-primary outcome of peak joint loading symmetry during gait, through fitting a separate GLMM. The main difference will be to include walking speed as an additional covariate, as justified in the research strategy. Secondary outcomes will also be analyzed using the same approach, each with its own GLMM.

An exploratory analysis will include Knee injury and Osteoarthritis Outcome Score (KOOS) pain scores as a (time-dependent) main effect, as well as their interaction with PAS, to evaluate whether this variable has an impact on intervention effects. This exploratory analysis will be repeated, but using participant-specific changes in KOOS pain scores, to examine how our primary outcomes (MVPA and peak load symmetry during walking) are associated with those changes.

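### The exploratory KOOS pain model asks an effect-modification question with pain measured after randomization; baseline KOOS pain is the score that can answer it

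*Protocol*

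**What the plan says.** Protocol 9.4 plans an exploratory model in which KOOS pain enters as a covariate that changes over time. The purpose of the added PAS term is given there: "as well as their interaction with PAS, to evaluate whether this variable has an impact on intervention effects". The SAP, under Analytic Techniques and Handling of Missing Data, has the same text: "pain scores as a (time-dependent) main effect, as well as their interaction with PAS". A second model in the same paragraph uses each participant's change in KOOS pain and speaks only of association with MVPA and symmetry.

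The rows of the model are follow-up rows: "the MVPA values at 8 weeks and at 6 months for a given patient will form their response vector for this model" (Protocol 9.4; the SAP agrees). KOOS is part of the assessment battery: "Measures will be collected at baseline, 3 months and 6 months by a trained research assistant blinded to randomization assignment" (Protocol 8.1), and the schedule in Protocol 1.3 marks it at Visit 1. Protocol 6.3 adds: "The participants will not be notified of randomization assignment until all baseline assessments are complete". Pain is also scored during treatment: "The KOOS pain subscale will also be assessed at each intervention visit, so that we can assess potential associations between pain and PA" (Protocol 8.1).

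The plan has one interaction of PAS with a baseline value, but that value is the baseline of the outcome being modelled. No interaction of PAS with baseline KOOS pain is planned.

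**The concern.** The stated purpose is to learn whether pain changes the effect of PAS. That calls for a characteristic fixed before PAS can act on it. Follow-up pain is not one. Protocol 2.2.2 lists less pain among the possible benefits, Protocol 2.2.1 rates short-term pain increases with activity as common, and knee symptoms are an exploratory outcome of the trial.

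Two mechanisms follow. Adjusting for follow-up pain removes whatever part of the PAS effect runs through pain (mediator adjustment). If pain and activity also share unmeasured causes, such as the pace of surgical recovery, holding follow-up pain fixed makes the arms non-comparable (collider bias). Neither is confounding in the usual sense, because allocation is randomized.

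At stake is how the result is read. The pain-adjusted PAS coefficient could be taken for an intervention effect, or the interaction for modification by starting pain, when the model identifies neither.

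**Working it through.** **Plan's own figures.** No figure is given for the KOOS analysis. The nearest is the SAP power table for 27 per group, two-sided 0.05. A two-sample t-test (noncentral t, 52 df, noncentrality d√(27/2)) gives 0.438, 0.581, 0.714, 0.822, 0.901 and 0.950 for 0.5 to 1.0 SD, so all six SAP entries reproduce. The copy in Protocol 9.1 shows 0.66 and 0.58 at 0.6 and 0.7 SD. Those two do not reproduce and are a separate matter.

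**Assumed inputs.** The documents give no size for the effect of PAS on pain, the pain-outcome slope, or shared causes. All values below are assumptions in SD units, with pain scored so that higher is better. The simulations use 4,000 trials of 54 participants per scenario and one follow-up visit, a simplification of the two-visit mixed model.

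**1. PAS term.** Let the total effect be 0.40, the PAS shift in pain δ, the pain-outcome slope b = 0.3, and λ the loading of a shared cause on both pain and outcome, with pain of unit variance within arm. Then

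adjusted PAS term = 0.40 − (b + λ²)·δ.

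| δ | λ = 0 | λ = 0.4 (b + λ² = 0.46) |
|---|---|---|
| 0.2 | 0.34 | 0.31 |
| 0.3 | 0.31 | 0.26 |
| 0.4 | 0.28 | 0.22 |
| 0.5 | 0.25 | 0.17 |

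Simulation agrees to about 0.01. The term can also depart from a true zero. In a second set-up, follow-up pain is 0.5 × baseline pain, plus 0.5 × a shared cause, plus noise of SD 0.7, giving variance 0.25 + 0.25 + 0.49 = 0.99. If PAS shifts pain by 0.5 and does nothing to the outcome, on which the shared cause also loads 0.5, the PAS term is −(0.25/0.99) × 0.5 = −0.13.

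**2. Interaction, uniform shift in pain.** In every scenario of the table, the simulated interaction stayed between −0.006 and 0.007, with type I error of 4.4% to 5.4%. A uniform shift does not create false modification.

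**3. Interaction, shift varying between patients.** Use the second set-up, with no effect of PAS on the outcome.
- If the effect of PAS on pain varies with the shared cause (coefficient −0.5), the loading in the PAS arm becomes 0. The pain slope is 0.25/0.99 = 0.25 in controls and 0 under PAS, a spurious interaction of −0.25. Across simulated variants it was −0.20 to −0.25, with type I error of 11% to 16.5%.
- With coefficient +0.5, the PAS-arm slope is 0.5/1.74 = 0.29, the interaction only about 0.03, and the type I error 5.3%.

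False modification is therefore possible, but it depends on how the effect on pain varies.

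**4. True modification by baseline pain of 0.40.** Follow-up pain carries only part of baseline pain, so the interaction reads 0.40 × 0.5/0.99 = 0.20 (simulated 0.20). With equal SDs at the two times the reading is 0.40 × r: 0.12 at r = 0.3 and 0.28 at r = 0.7. This happens even if PAS does not change pain (simulated 0.21). It is the wrong variable for the question, not a bias created by PAS.

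**5. Same question with baseline pain.** The interaction read 0.40 to 0.41 when the truth was 0.40 and about 0 when it was 0, with type I error of 4.8% to 5.5%. The PAS term recovered the total effect (0.50 for 0.50).

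**6. Precision of the baseline version.** With 27 per group and residual SD 1, the standard error of the slope difference is √(2/27) = 0.27 and the 95% half-width is about 2.01 × 0.272 = 0.55. Power is about 0.19, 0.44 and 0.82 for slope differences of 0.3, 0.5 and 0.8. For a 0.5 SD difference in effect between two equal pain subgroups it is about 0.15.

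**The case against.** The strongest reply is that this is one analysis, labelled exploratory, in a pilot. Intervention effects come from contrasts in the primary model, which contains no KOOS term, and nothing says the pain-adjusted PAS coefficient will be reported as the effect. The illustrated shifts in that coefficient (0.06 to 0.23 SD) are smaller than its standard error of roughly 0.25 to 0.28 at this sample size. The protocol also gives association between pain and activity as its reason for scoring pain at intervention visits, and the change-in-pain model is already worded as association. All of that stands, and it limits the point to one clause.

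A reader might infer more: that the model will report modification where none exists, or that its result will be used to target or refine PAS. The documents support neither. False modification needs an effect of PAS on pain that varies between patients, and no passage gives any size for that effect. Refinement of PAS is tied to acceptability feedback (Protocol 4.1, aim 3b, and 9.4), and planning of the larger trial's sample size to the primary-model contrasts and correlations (Protocol 9.4).

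It is also fair that baseline pain answers a narrower question. It is measured during the course of physical therapy, before PAS begins at the last two visits, so it may differ from pain when PAS starts.

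What does not stand is the exploratory label as a defence. It limits how firmly a result is stated; it does not change what the coefficient estimates. The clause claims a reading about intervention effects that the model cannot supply.

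**Conclusion.** The concern holds in a limited form. Both documents condition on pain measured after randomization to answer an effect-modification question, although a score taken before assignment is disclosed is available. If PAS changes pain, the PAS term is not the total effect; in the assumed scenarios 0.40 SD reads 0.34 to 0.25, or 0.31 to 0.17 with a shared cause. The interaction does not measure modification by starting pain: 0.40 reads about 0.20 at a baseline to follow-up correlation near 0.5. If PAS affects neither pain nor the outcome, neither term is biased.

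These sizes rest wholly on assumed inputs. The primary contrasts are untouched, and the consequence is confined to how one exploratory result is interpreted.

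**What to change.** Amend the KOOS paragraph in Protocol 9.4 and the matching SAP paragraph.

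- **Effect modification.** Enter baseline KOOS pain (Visit 1) as a main effect with its interaction with PAS, for MVPA and for load symmetry. Report the interaction as an estimate with a 95% confidence interval, and say that precision is low at about 27 per group.
- **Follow-up and change-in-pain models.** Keep them as descriptive associations between pain and MVPA or symmetry, and state that their PAS and interaction terms are not read as intervention effects.
- **Pairing of visits.** State which KOOS value goes with the first follow-up outcome. The model text says 8 weeks, while Protocol 1.3 and 8.1 place the assessment at 3 months. Both are after randomization.

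The cost is wording only, since the baseline score is already collected. The small downside is that baseline pain precedes the start of PAS and shows only whether the effect differs by starting pain; the retained descriptive models cover how pain during follow-up relates to activity.

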10 SUPPORTING DOCUMENTATION AND OPERATIONAL CONSIDERATIONS

10.1 REGULATORY, ETHICAL, AND STUDY OVERSIGHT CONSIDERATIONS 10.1.1 INFORMED CONSENT PROCESS

10.1.1.1 CONSENT AND OTHER INFORMATIONAL DOCUMENTS PROVIDED TO PARTICIPANTS

Consent forms describing in detail the study intervention, study procedures, and risks will be given to the participant and written documentation of informed consent will be completed prior to starting the study intervention. The following consent materials are submitted with this protocol: Adult Consent Form.

10.1.1.2 CONSENT PROCEDURES AND DOCUMENTATION

Once a potential participant meets the medical record and telephone screening criteria for eligibility, and is interested in participating, a study team member will email or mail the potential participant a copy of the informed consent form and HIPAA for them to review. The study team member will set up a time to call the potential participant no more than 24 hours before the baseline visit to conduct the COVID-19 wellness screening. During the phone call, the study team member will review the IRB approved consent form with the potential participant and provide an opportunity for him/her to ask any questions that they may have about the research study.

We will use a UNC IRB approved consent form with included language that satisfies the HIPAA requirements and outlines the protection of health information utilized in the study. No other study activities will occur until the consent process is completed.

We anticipate this process to take approximately 20 minutes, but this time will not be limited should a participant have additional questions or concerns regarding the study. During this phase of the consent process, it will be stressed that the participant is not obligated to participate in the study, that participation is completely voluntary, and that he/she may withdrawal from the study at any time without penalty. Also, potential risks from participating in the study will be outlined in the consent form, as are the measures taken to protect against study specific risks. Once the information in the consent from is fully reviewed and understood by the individual, he/she will be asked to decide at that time if they would like to voluntarily participate in the research study. If the individual does choose to participate in the study, they will be asked to print, sign and date the consent form and HIPAA, and bring the documents with them to the baseline visit. If the participant is unable to print or bring the documents, copies will be available at the baseline visit for them to complete. Both the individual and the study team member will sign and date the consent form. Each enrolled participant will then receive a signed copy of their consent form to keep for their records.

If after reviewing the consent form, the potential participant is not sure they would like to participate in the study at this time, they may choose to consider the study further at home, and then contact the study team if they decide later that they would like to participate.

Participants will only be included if they have capacity to give legally effective consent. Additionally, this study will only recruit participants whom are English speakers.

Version 11.0 6 October 2022

